3. ANALYSIS POPULATIONS

In accordance with guidance from the International Conference of Harmonization of Technical Requirements for Registration of Pharmaceuticals for Human Use (ICH) guideline ICH E9 Statistical Principles for Clinical Trials (ICH, 1998), below are the patient populations defined for statistical analysis. The Safety Analysis Set will be the main analysis set for exposure/compliance, clinical safety and efficacy. Additional analysis sets are defined for pharmacokinetic (PK), anti-drug (evinacumab) antibody (ADA).

3.1. Safety Analysis Set

The safety analysis set (SAF) includes all patients who was enrolled and received at least 1 dose or part of a dose of open-label study treatment in this study. The SAF will be the main analysis set for exposure/compliance, clinical safety and efficacy.

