10.3. Analysis Sets

10.3.1. Safety Analysis Set

The safety analysis set (SAF) includes all patients who received at least 1 dose or part of a dose of open-label study treatment in this study. The SAF will be the main analysis set for exposure/compliance, clinical safety and efficacy.

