1.2.3. Modifications from the Statistical Section in the Final Protocol

N/A.

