3.2. Efficacy Analysis Set

The SAF will be the main analysis set for efficacy.

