3.3. Pharmacokinetic (PK) Analysis Set

The PK analysis set includes all treated patients who received any study drug and who had at least 1 non-missing result of evinacumab concentration following the first dose of study drug.

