4.5. Patient Disposition

Patient disposition will include the description of patient status at major milestone decisions in the study, as well as the patient analysis populations.

For patient study status, patient milestone categories are defined below. As applicable, percentages will be calculated using a denominator of the number of patients treated with open-label study treatment, with two exceptions. Specifically, the two exceptions will be for the screened and screen failure categories, which will not have associated percentages shown.

- The total number of screened patients: defined as originally having met the inclusion criteria and signed the ICF
- The total number of patients failed screening
- The total number of patients enrolled, defined as all screened patients with a treatment kit number allocated and recorded in the IVRS database, regardless of whether the treatment kit was used.

- The total number of patients enrolled but not receiving study treatment.
- The total number of patients enrolled and receiving study treatment.
- The total numbers of patients who have participated in a previous evinacumab study (i.e., R1500-CL-1331 and R1500-CL-1629), or evinacumab-naïve patients with HoFH.
- The total number of patients who completed the OLTP as collected on the End of Treatment - Evinacumab e-CRF.
- The total number of patients who prematurely discontinued study treatment during the OLTP, and the reasons for discontinuation collected on the End of Treatment - Evinacumab e-CRF.
- The total number of patients ongoing in OLTP (applicable for the interim analyses)
- The total number of patients who complete the last study follow-up visit (i.e. Follow-up week 24).

The following patient populations for analyses are listed below:

- Safety (SAF) Analysis Set
- Efficacy Analysis Set (same as SAF)
- Pharmacokinetic (PK) Analysis Set
- Immunogenicity (ADA and NAb) Analysis Sets

The following patient listings will provide the details from the patient disposition table.

- A listing of patients treated but not enrolled, patients enrolled but not treated.
- A listing of patients prematurely discontinued from treatment, along with reasons for discontinuation.

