5.8. Analysis of Safety Data

Safety summaries for the study will be presented by patient group for the study in the safety analysis set, and again for the subpopulation of adolescent patients. No formal inferential testing will be performed. Summaries will be descriptive in nature.

All safety analyses will be performed using the baseline definitions described in Section 6.1.

General common rules

All safety analyses will be performed, unless otherwise specified, using the following common rules:

- Safety data in patients who do not belong to the safety analysis set (e.g., exposed but not enrolled) will be listed separately.
- The potentially clinically significant value (PCSV) values are defined as abnormal values considered medically important by the Sponsor according to predefined criteria/thresholds based on literature review and defined by the Sponsor for clinical laboratory tests and vital signs (PCSV version dated January 2009 [Appendix 10.4]).

Considering that the threshold defined in the PCSV list for monocytes and basophils can be below the ULN, the following PCSV criterion will be used for the PCSV analysis of monocytes and basophils:

- PCSV criterion for monocytes: >0.7 Giga/L or >ULN (if ULN ≥0.7 Giga/L).
- PCSV criterion for basophils: >0.1 Giga/L or >ULN (if ULN ≥0.1 Giga/L).

- PCSV criteria will determine which patients had at least 1 PCSV during the TEAE period, taking into account all evaluations including unscheduled or repeated evaluations.
- The treatment-emergent PCSV denominator by patient group for a given parameter will be based on the number of patients assessed for that given parameter at least once during the TEAE period.
- All measurements, scheduled or unscheduled, fasting or not fasting, will be assigned to Global Analysis Windows defined in Appendix 10.2 /Table 1 in order to provide an assessment for the screening visit through follow-up visit time points.
- For quantitative safety parameters including central laboratory measurements and vital sign scores, descriptive statistics will be used to summarize observed values and change from baseline values by visit.
- Open-label treatment period (OLTP): The treatment period used for quantitative analysis of laboratory and vital signs data in the open-label study period is defined from the day after the first dose of open-label study treatment to the day of the last dose of open-label study treatment + 28 days.

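### The SAP adds an enrolment condition to the protocol's dosed-only safety set without declaring it, so a patient dosed without an IVRS kit record falls out of the main safety, exposure and efficacy tables

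*SAP*

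**What the plan says.** Protocol 10.3.1 states that the SAF "includes all patients who received at least 1 dose or part of a dose of open-label study treatment in this study". The statistical plan in the protocol synopsis gives the same definition. Neither place mentions enrolment.

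SAP 3.1 states that the SAF "includes all patients who was enrolled and received at least 1 dose or part of a dose" of open-label treatment. SAP 3.2 adds: "The SAF will be the main analysis set for efficacy".

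SAP 4.5 gives the terms that the added word relies on. Enrolled patients are "defined as all screened patients with a treatment kit number allocated and recorded in the IVRS database", whether or not the kit was used. Screened patients are "defined as originally having met the inclusion criteria and signed the ICF". Protocol 10.4.1 has the same two definitions, but only as rows of the disposition table. The protocol's SAF does not use them.

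SAP 5.8 sets the handling rule: "Safety data in patients who do not belong to the safety analysis set (e.g., exposed but not enrolled) will be listed separately". SAP 4.5 and 5.5 also plan exception listings of patients treated but not enrolled.

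SAP 1.2.3, headed "Modifications from the Statistical Section in the Final Protocol", is answered N/A.

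**The concern.** This is a single-arm, descriptive, long-term safety study. Its primary endpoint is the incidence and severity of treatment-emergent events, and the SAF supplies the denominators. A patient who received drug is exposed whether or not the kit allocation was recorded, and that patient's events and exposure time belong in the summaries. Under the protocol's definition no dosed patient can be outside the SAF. Under the SAP's definition some can, and the SAP makes explicit provision for them.

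The stakes are highest in adolescents. Their long-term safety is a primary objective in its own right, and only about 14 are planned, so one patient more or less is visible in every percentage.

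**Working it through.** There is no planned figure to reproduce. Both documents say that no sample size calculation was performed. The check is a comparison of definitions, followed by an illustration of size.

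**Step 1: the sets side by side**

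| Set | Source | Condition for entry |
|---|---|---|
| SAF | Protocol 10.3.1 | Any full or partial open-label dose |
| SAF | SAP 3.1 | Enrolled, and any full or partial open-label dose |
| PK set | SAP 3.3 | Treated, with a concentration result after first dose |
| ADA set | SAP 3.4.1 | Treated, with an ADA result after first dose |

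The PK entry begins "The PK analysis set includes all treated patients who received any study drug". It and the ADA entry have no enrolment condition. By these definitions a dosed patient without a kit record can be in the PK and ADA sets but not in the SAF.

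**Step 2: who is lost**

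Enrolled = screened and kit number recorded in IVRS (SAP 4.5). Hence:

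- Dosed, kit recorded: in the SAF under the protocol. In the SAF under the SAP as well, provided the patient counts as screened.
- Dosed, no kit recorded: in the SAF under the protocol, outside it under the SAP. This follows on any reading of the definitions.

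**Step 3: where the loss shows**

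SAP 5.8.1 uses the SAF as the denominator for adverse event percentages. SAP 5.6 and 5.7.1 use it for exposure and lipid changes. SAP 4.5 bases disposition percentages on patients treated. The disposition and adverse event denominators can therefore differ within one report. The listing rule in SAP 5.8 concerns safety data, and the SAP states no counterpart for lipid data.

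**Step 4: size**

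Inputs: N = 120 in total and 14 adolescents, both approximate (SAP 2.2; Protocol 10.2). The number of affected patients, k, is in neither document. I assume k = 0 to 3.

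Share of the set per patient: 1/120 = 0.8%; 1/14 = 7.1%.

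The worst case for an incidence is that every excluded patient had the event and nobody else did. The protocol set then gives k/N and the SAP set gives 0/(N − k). Exact (Clopper-Pearson) 95% limits are the 0.025 quantile of Beta(x, n − x + 1) and the 0.975 quantile of Beta(x + 1, n − x), with a lower limit of 0 when x = 0.

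| N | k | Protocol set | SAP set |
|---|---|---|---|
| 14 | 1 | 1/14 = 7.1% (0.2 to 33.9) | 0/13 = 0% (0 to 24.7) |
| 14 | 2 | 2/14 = 14.3% (1.8 to 42.8) | 0/12 = 0% (0 to 26.5) |
| 14 | 3 | 3/14 = 21.4% (4.7 to 50.8) | 0/11 = 0% (0 to 28.5) |
| 120 | 1 | 1/120 = 0.8% (0.0 to 4.6) | 0/119 = 0% (0 to 3.1) |
| 120 | 2 | 2/120 = 1.7% (0.2 to 5.9) | 0/118 = 0% (0 to 3.1) |
| 120 | 3 | 3/120 = 2.5% (0.5 to 7.1) | 0/117 = 0% (0 to 3.1) |

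If the excluded patient did not have the event, the change is small. For example, 3/14 = 21.4% becomes 3/13 = 23.1%. With k = 0 nothing changes.

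**The case against.** The strongest reply is that this is a drafting slip with little practical reach. Protocol 11.2 names the IVRS/IWRS system for study drug supply, so dosing without a kit record should be rare. If it happens, the SAP discloses it through the exception listings and the separate listing of safety data. No formal testing is planned, so no error rate is at risk. All of this stands, and it limits the size of the point. It does not remove the conflict: a listed patient is still missing from numerators and denominators, and the SAP says it makes no change to the protocol's statistical section.

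Three stronger readings are tempting, and the documents do not support them.

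- A reader might infer that a dosed patient later found to have failed an inclusion criterion is dropped, because enrolled patients must first be screened and screened patients are "defined as originally having met the inclusion criteria and signed the ICF". On a strictly literal reading a dosed patient who did not meet a criterion could be excluded. But the word 'originally' can equally mean judged eligible at entry, which would keep that patient in. The direct test of enrolment is the kit record, and SAP 4.6 and 5.6.2 review and summarise protocol deviations without removing anyone from the SAF. An unconfirmed genotype is also a poor example, since inclusion criterion 2 can be met on clinical grounds alone.
- A reader might take SAP 5.8 as confirming that eligibility failures are excluded. It gives only exposure without enrolment as its example and says nothing about inclusion criteria.
- A reader might conclude that screen failures are undercounted. SAP 4.5 gives patients who failed screening their own row and does not define them as part of the screened count, so an undercount is not shown.

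**Conclusion.** The point holds for the enrolment condition. SAP 3.1 departs from Protocol 10.3.1, SAP 5.8 carries the departure through, and SAP 1.2.3 does not declare it. A patient dosed without an IVRS kit record would be left out of the SAF and so out of the main safety, exposure and efficacy tables. Exclusion for failing an inclusion criterion is a possible literal reading and no more than that.

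The practical size is probably small. The number affected is unknown and may be zero; the range of 0 to 3 is my assumption. One patient would be 0.8% of 120 or 7.1% of 14. The 7-point shift in an adolescent incidence also needs that patient to be an adolescent and to have had the event. The change is still worth making, because it costs almost nothing and keeps every exposed patient in the primary safety tables.

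**What to change.** 1. In SAP 3.1, delete 'was enrolled and', so that the SAF is defined by receipt of any full or partial open-label dose, as in Protocol 10.3.1.
2. In SAP 5.8, remove the example that places dosed-but-not-enrolled patients outside the SAF.
3. Keep the exception listings in SAP 4.5 and 5.5 as a supplement, with those patients also counted in the SAF tables.

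Once the first edit is made, the wording of 'screened' and 'enrolled' in SAP 4.5 no longer affects who is in the SAF, so its ambiguity ceases to matter for the main tables.

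The cost is two wording edits to the SAP, with no protocol change, no added data and no extra analysis.

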3.2. Efficacy Analysis Set

The SAF will be the main analysis set for efficacy.

3.3. Pharmacokinetic (PK) Analysis Set

The PK analysis set includes all treated patients who received any study drug and who had at least 1 non-missing result of evinacumab concentration following the first dose of study drug.

3.4. The Immunogenicity Analysis Sets

3.4.1. The Anti-evinacumab Antibody Analysis (ADA) Set

The anti-evinacumab antibody (ADA) analysis set includes all treated patients who received any study drug and who had at least 1 non-missing ADA result following the first dose of study drug.

3.4.2. The Neutralizing Antibody (NAb) Analysis Set

The NAb analysis set includes all patients who received any study drug and who are negative in the ADA assay or with at least 1 non-missing result in the NAb assay. Patients who are ADA negative are set to negative in the NAb analysis set.

4. ANALYSIS VARIABLES

4.1. Demographic and Baseline Characteristics

For each patient, demographic and baseline characteristics will be obtained according to the definition of baseline specified in Section 6.1.

According to the protocol, patients who completed the EOS visit in the previous evinacumab study within 7 days of the baseline/day 1 visit for this open label study do not have to undergo the screening visit and may enroll directly into this study if they fulfill all of the inclusion criteria and none of the exclusion criteria. Therefore, the EOS visit from the previous study can serve as

the baseline/day 1 visit for this open-label study and overlapping assessments do not need to be repeated in this study. Such data will be rolled into the R1500-CL-1719 database and will be used in the calculation of the baseline assessments.

Baseline assessments and procedures that do not overlap with assessments at the EOS visit of the previous study will be performed after all EOS assessments and procedures have been completed in the previous evinacumab study.

All baseline safety and efficacy parameters (apart from those listed below) will be presented along with the summary statistics in the safety and efficacy sections.

The following variables will be summarized:

Demographic Characteristics

- Sex (Male, Female)
- Race (White, Black or African American, Asian, American Indian or Alaska Native, Native Hawaiian or Other Pacific Islander, Not Reported, Other)
- Age in years (quantitative and qualitative variable: ≥ 12 to < 18 , ≥ 18 to < 45 , ≥ 45 to < 65 , ≥ 65 to < 75 , and ≥ 75 years; and < 65 , and ≥ 65 years)
- Ethnicity (Hispanic or Latino, Not Hispanic or Latino, Not reported, Unknown)

Baseline Characteristics

- Baseline Weight (kg)
- Baseline Height (cm)
- Baseline Body mass index (BMI) in kg/m^2 (quantitative and qualitative variable defined as < 30 , ≥ 30)
- Smoking Status (never, former, and current smoker)
- Current alcohol consumption (yes/no)
- Current apheresis treatment (yes/no)
- If apheresis occurring: schedule from the e-CRF (i.e. QW, Q2W, Q3W)
- Tanner staging (for adolescent patients)

Baseline Disease Characteristics

- Lipid parameters - quantitative variables for all efficacy parameters
- HbA1c both quantitative variable and qualitative variable defined as: $< 5.7\%$, $\geq 5.7\%$ to $< 6.5\%$, $\geq 6.5\%$
- hs-CRP
- LDL-C: < 70 , ≥ 70 to < 100 , ≥ 100 to < 130 , ≥ 130 to < 160 , ≥ 160 to < 190 , ≥ 190 mg/dL (< 1.81 , ≥ 1.81 , < 2.59 , ≥ 2.59 to < 3.37 , ≥ 3.37 to < 4.14 , ≥ 4.14 to < 4.91 , ≥ 4.91 mmol/L)
- Fasting TG: < 150 , ≥ 150 to < 200 , ≥ 200 mg/dL, and category ≥ 150 mg/dL for mixed dyslipidaemia (< 1.7 , ≥ 1.7 to < 2.3 , ≥ 2.3 mmol/L, and category ≥ 1.7 mmol/L),

- Lp(a): <30, ≥30 to <50, ≥50 mg/dL, and category ≥30 mg/dL (<75, ≥75 to <125, and ≥125 nmol/L, and category ≥ 75 nmol/L)
- Mutation type (e.g. homozygous [defective/defective or negative/negative mutations], compound heterozygous [defective/defective, defective/negative or negative/negative mutations], and double heterozygous [defective/defective, defective/negative or negative/negative])
- LDLR activity status (null/null [LDLR activity ≤15%], not null/null [LDLR activity >15%])

4.2. Medical History

As applicable, patient medical history, pre-listed or not in the e-CRF will be dictionary coded by primary system organ class and preferred term using the Medical Dictionary for Regulatory Activities (MedDRA), specifically the MedDRA version in effect at the time of the first database lock. The medical history of interest collected on dedicated and pre-listed e-CRFs is: cardiovascular history and risk factors, primary and secondary CVD prevention, CV risk factors categorized by high and very high risk, hyperlipoproteinemia disease history (including LMT therapies), and apheresis history.

Medical history of interest is defined as the occurrence of these diseases:

1. Coronary heart disease (CHD)
2. CHD risk equivalents
3. Cardiovascular (CV) risk factors other than hypercholesterolemia (hypertension, type 2 diabetes, type 1 diabetes, family history of premature CHD).
4. Family history of type 2 diabetes

CHD and CHD risk equivalents will be derived from the respective e-CRF as follows:

5. Coronary heart disease (CHD) (regardless if it is ongoing or not) is defined as the occurrence of at least one of the following events:
 - Acute myocardial infarction
 - Silent myocardial infarction
 - Angina (chronic stable or unstable)
 - Coronary revascularization procedure (e.g. PCI, CABG)
6. CHD risk equivalent (regardless if it is ongoing or not) is defined as the occurrence of at least one of the following events:
 - Peripheral arterial disease (PAD)
 - Ischemic stroke
 - Chronic kidney disease (CKD)
 - Known history of diabetes mellitus (type 1 or 2) AND 2 or more additional risk factors among:

- History of ankle-brachial index ≤ 0.90
- History of hypertension
- History of microalbuminuria or macroalbuminuria
- History of proliferative diabetic retinopathy
- Known family history of premature CHD

Secondary CVD prevention is defined as patients with any of the following history of CVD (other patients will be classified as primary CVD prevention):

- History of CHD (as defined above)
- History of ischemic stroke
- History of PAD with severity criteria defined as one of the following events:
 - PAD and ankle brachial index ≤ 0.90
 - Peripheral revascularization procedure (angioplasty, stenting) for PAD
 - Thrombolysis for PAD
 - Peripheral revascularization surgery (arterial bypass) for PAD

CV Risk Factors are defined for this study as high risk and very high risk below.

- Very high CV risk patients are defined as patients with CHD or CHD risk equivalents.
- High CV risk patients are defined as all other patients.

Hyperlipoproteinemia disease history will be assessed through diagnosis of HoFH, time from diagnosis to the first open-label evinacumab treatment administration date (years), method of diagnosis of HoFH (genotyping, clinical diagnosis), lipid modifying therapies history reported in the “History of Hypercholesterolemia/Statin Use” e-CRF page.

Apheresis history information will include the procedure frequency, and treatment technique.

4.3. Prior and Concomitant Medications

All medications (including statin, non-statin LMT, and CV) taken from the time of informed consent to the final study visit, including medications that were started before the study and are ongoing during the study, will be reported in Concomitant Medications CRF.

All medications will be dictionary coded using the World Health Organization-Drug Dictionary (WHO-DD) to both an anatomic category and a therapeutic category, with the version in effect at the time of the first database lock. Drug names will be matched to respective Anatomical-Therapeutic-Chemical (ATC) classification, although a drug can be matched to more than one ATC classification (i.e. patients can be counted in several categories for the same medication). Prior medications, concomitant medications, and post-treatment medications are defined below.

- Prior medications are defined as medications for which the stop date is before the date of the first study treatment administration.

- Concomitant medications are defined as medications that are administered to the patients during the study treatment period. Specifically:
 - Start date of the concomitant medication is on or after the first study treatment administration in study treatment period (\geq OLTP Day 1); **or**
 - Start date of the concomitant medication is before the first study treatment administration in study treatment period and is “Ongoing” during the treatment emergent period; **or**
 - Start date of the concomitant medication is before the first study treatment administration in study treatment period, and the end date is on or after the first study treatment administration in study treatment period (\geq OLTP Day 1).

The concomitant medication treatment emergent period is defined as:

- For concomitant medications in the OLTP, the treatment emergent period is defined from the first day of open-label study treatment administration to the last day of open-label study treatment +168 days.

Note: In the case the start date is before first study treatment administration and both ongoing status and stop date are missing, the medication will be assumed to be concomitant.

- Post-treatment medications are defined as medications for which the start date is after last date of study treatment administration +169 days (\geq last study treatment +169 days).

